### **7.5.1 Baseline**

The prevalence of baseline genetic variations, i.e. the number of subjects with baseline genetic variations, will be tabulated in frequency outputs (n, %), based on Sanger and NGS data (1% and 15% cut-off), and the genetic variations will be listed for all subjects.

Subgroup analysis by the presence of baseline genetic variations will be tabulated to evaluate the impact on treatment response (see Section 5 for treatment response categories).

---

### 7.5.2 Post-Baseline

- ***Time of Viral Breakthrough (if applicable)***

For subjects with viral breakthrough, the incidence of treatment emergent (NGS) and treatment enriched genetic variations will be tabulated in frequency outputs (n, %) and the genetic variations will be listed for all subjects with post-baseline sequencing data.

The return to baseline for subjects with viral breakthrough and treatment-emergent genetic variations at time of viral breakthrough will be tabulated in frequency outputs based on Sanger and NGS data, as well as the treatment-emergent genetic variations in subjects who did not return to baseline.

- ***Other Post-Baseline***

The prevalence of genetic variations at other time points will be tabulated in frequency outputs (n, %), based on Sanger and NGS data (1% and 15% cut-off), and the genetic variations will be listed for all subjects. Time points of specific interest are end-of-treatment and end-of-study.

### 7.5.3 Over the Study Period

For all subjects, listings with relevant baseline disease and demographic characteristics, session info, all genetic variations at baseline, at time of viral breakthrough (if applicable), at end of JNJ-379 treatment, and at end of study will be generated.

For all subjects, listings with relevant baseline disease and demographic characteristics, session info, and aggregate post-baseline sequence data over the whole treatment period, and aggregate post-baseline sequence data over the whole study period will be generated.

#### 7.1.1 Other analysis

Sequence variations will be analyzed and reported on both the nucleotide level (such as changes in the basal core promoter and pre-core region) as well as on amino acid level. In the sequence analysis, sequences will be mapped to the respective genotype specific reference sequences after which nucleotide level changes and amino acid substitutions

---

will be annotated compared to the respective genotype specific reference (see Table in section 7.2). In addition, the X02763 (HBV genotype A), which is the master reference sequence of the HBV, will be used as universal reference sequence.

All NGS data will be collected using a nucleotide level and amino acid read frequency cut-off of  $\geq 0.01$ .

For the analysis of baseline nucleotide level changes and/or amino acid substitutions in terms of prevalence and impact on treatment outcome, a read frequency cut-off of  $\geq 0.15$  will be used.

The analysis of treatment-emergent nucleotide level changes or amino acid substitutions will consider nucleotide level changes or amino acid substitutions absent at baseline ( $<0.01$  read frequency) but present at a read frequency of  $\geq 0.15$  at later time points.

Virology analyses based on NGS data will also evaluate treatment-enriched nucleotide level changes and amino acid substitutions, defined as present at baseline with a read frequency  $\geq 0.01$  but  $<0.15$  and with an increase in read frequency of at least 0.15 post-baseline.

A minimum increase in read frequency of 0.15 compared to baseline excludes small, potentially technical variations in the read frequency of minority nucleotide level changes and amino acid substitutions which are not expected to have clinical relevance. In addition, for subjects with treatment failure nucleotide level changes and amino acid substitutions detected with a read frequency  $\geq 0.01$  at baseline, at time of failure and at end of study will be described in a listing. The persistence of treatment-emergent nucleotide level changes and amino acid substitutions will be evaluated using a cut-off of  $\geq 0.15$  and  $\geq 0.01$ .

## **8. PATIENT REPORTED OUTCOMES ANALYSIS**

The impact of HBV treatment on subjects, including functioning and HRQoL will be assessed using PROs at predefined time points in the ITT population.

- 5-level EuroQol 5-Dimension (EQ-5D-5L) Visual Analog Scale score and Index Score;
- Hepatitis B Quality of Life Instrument (HBQOL).

---

- Medical Outcomes Study Cognitive Functioning Scale-Revised (MOS-CFS Cog-R);
- Short Form 36 version 2 (SF-36v2) 8 Domain Scores/Subscales, Physical Component Summary and Mental Component Summary scores

## **8.1. Level EuroQol 5-Dimension (EQ-5D-5L)**

See [APPENDIX](#) for a representative of 5-level EuroQol 5-Dimension (EQ-5D-5L) Visual Analog Scale score and Index Score full questionnaire.

### **8.1.1 Definition**

The EQ-5D questionnaire will be analyzed in 3 ways:

- EQ-5D descriptive system scores (5 scores reflecting each of the 5 dimensions see [APPENDIX](#) for a representative example of the EQ-5D-5L.  
an assessment that evaluates a subject's self-rated health state on 5 dimensions (mobility, self-care, usual activities, pain/discomfort, anxiety/depression) with 5 possible levels (no problems (level code = 1), slight problems (level code = 2), moderate problems (level code = 3), severe problems (level code = 4), extreme problems (level code = 5)).
- EQ-5D VAS a continuous score ranging from 0 to 100 (with a possible range from 0 [worst imaginable health] to 100 [best imaginable health]);

This information can be used as a quantitative measure of health outcome as judged by the subject.

- EQ-5D Valuation Index The information of the 5 dimensions of the descriptive system summarized into one index. (a weighted scoring of the 5 dimensions scores with a possible range from 0 to 1);

EQ-5D Valuation index summarizes the information of the 5 dimensions of the descriptive system as below.

- a. Assign the level code 1, 2, 3, 4 and 5 to each level of the 5 dimensions (see [APPENDIX](#))

---

b. Create a health state for each patient-time point combination. A health state is a combination of 5 level codes; one level code for each dimension. The dimensions are ordered as described in the [APPENDIX](#).

E.g. health state 12543 indicates ‘no problems in walking about, slight problems washing or dressing myself, unable to do my usual activities, severe pain or discomfort, moderately anxious or depressed’.

c. Assign an index value to each health state as defined in the appendix of Data Presentation Specifications (DPS) documents.

EQ-5D health state is converted to a single summary index by applying a formula that essentially attaches weights to each of the levels in each dimension. The algorithm is based on the valuation of EQ-5D health states using the UK TTO (=time trade-off method) based value set. Based on the origin of the subjects, another method can also be used (UK crosswalk-based values).

### **8.1.2 Missing data**

1) If – for a questionnaire – one (or more) dimensions of the descriptive system are missing, then

- The EQ-5D VAS will be tabulated if not missing
- The valuation index will not be tabulated
- The non-missing dimensions of EQ-5D descriptive system will be summarized

2) If – for a questionnaire – the EQ-5D VAS is missing then the EQ-5D descriptive system and validation index will be tabulated if complete.

## **8.2. Hepatitis B Quality of Life (HBQOL)**

See [APPENDIX 1](#) for a representative example of the HBQOL version 1 full questionnaire.

There are 31 scored items included in the HB-QOL, including 13 items regarding how HBV makes patients feel socially or mentally (F1-F13), 15 items regarding HBV-related concerns (C1-C15), and 3 items regarding HBV-related physical impacts.

For HBQOL, scores will be calculated as below:

---

Each item is scored on a 5-level response scale ranging from 1 through 5. Each response is transformed along a 0 to 100-point scale, where lower scores denote less HRQOL impact, and higher scores denote more HRQOL impact (i.e. 0=best score; 100=worst score), as follows:

- Level 1 – 0 points
- Level 2 – 25 points
- Level 3 – 50 points
- Level 4 – 75 points
- Level 5 – 100 points

**The items are combined to form 7 subscales, as follows:**

Psychological Well-Being (8 Items), Anticipation Anxiety (6 Items), Vitality (5 Items), Stigma (6 Items), Vulnerability (3 Items), Transmission (3 Items) and Viral Response (4 Items).

**The global score that reflects the results on all 31 items.**

Each subscale score is simply calculated as the average score among the items included in that subscale. The global score is simply the average score among all the items in the HBQOL.

For example, consider these sample scores for items in the vulnerability scale:

Item Number	Item Name	Raw Score	Scaled Score
C13	Concern eat	2	25
C6	Concern sick easily	4	75
C8	Concern medicines	3	50
		Average	50

The score on this subscale is 50 out of a possible score of 100, where higher scores denote more severe negative impact of HBV on HRQOL. The scores will be derived if at least 50% of the items or domain scores are available respectively, no imputation of missing data will be performed.

---

### 8.3. Medical Outcomes Study Cognitive Functioning Scale-Revised (MOS-CFS Cog-R)

See [APPENDIX 1](#) for a representative example of the MOS-CFS Cog-R full questionnaire. Scores will be derived and delivered by a vendor (OPTUM), in CSV file and added in ADAM datasets

#### 8.3.1 Definition

The MOS CSF is 6 dimensions questionnaire with 5 different scales

Response choice for questions	Questionnaire Coded Value (scale)	Final Value use for scoring
All of the time	1	1
Most of the time	2	2
Some of the time	3	3
little of the time	4	4
None of the time	5	5

All scales can be scored (using a scoring algorithm such as [RAND or other](#) ) so that a high score defines a more favorable health state. scales are scored in five steps:

- Data-cleaning (e.g., changing out-of-range values (values that are lower or higher than an item's minimum and maximum value) to missing),
- Transforming item scores linearly to a common metric with a possible range of 0-100 => New transformed= (old scale-lower-scale) \*100/(5-1)=(old scale-1)\*25
- Averaging across items in the same scale => Average (New Transformed)

The scores will be derived using OPTUM scoring software (Third party vendor)

#### 8.3.1 Missing data

The score estimation techniques, we will use all missing data, OPTUM scoring software is able to input the missing scale scores and component scores and estimate the score even some items are missing.

---

## 8.4. Short Form 36 version 2 (SF-36v2)

See [APPENDIX 1](#) for a representative example of the SF-36v2 full questionnaire.

Scores will be derived and delivered by a vendor (OPTUM), in CSV file and added in ADAM datasets

### 8.4.1 Definition

The short form of SF-36 is a 11-item questionnaire that measures eight multi-item dimensions of health (HRQoL), where participants self-report on item in a domain scale that have between 2-6 response choices per item.

The short form of SF-36 can be interpreted using T-scores from the 8 domain scales and 2 summary scores defined below:

The physical component (PCS):

- Physical functioning (10 items: in question 3)
- Role limitations due to physical problems (4 items: question 4)
- Bodily pain (2 items: questions 7 and 8)
- General health perception (5 items: questions 1 and 11 a to 11d).
- Energy/vitality or Fatigue (4 items: questions 9 a, 9e, 9g, and 9i)

The mental component (MCS):

- Role limitations due to emotional problems (3 items: questions 5a, 5b, and 5c)
- General Mental health (5 items: questions 9b, 9c, 9d, 9f, and 9h),
- Social functioning (2 items: questions 6 and 10)

A scoring algorithm will be used to convert the raw scores into the eight dimensions listed above. The total domain scores of domain scales will be transformed into a range from zero where the respondent has the worst possible health to 100 where the respondent is in the best possible health. The scores (0-100) will then be standardized using means and standard deviation from 2009 U.S. general population and converted to norm-based scores using a T-score transformation (mean = 50, SD = 10). Two aggregate component scores will be derived as linear combination of the standardized (2009 U.S. norm) scores using weights from principal component analysis. Each aggregate component score will be transformed to the corresponding PCS T-score and MCS T-score (mean = 50 and SD = 10)

---

The domain scale scores and component summary scores will be calculated using the Quality Metric Health Outcomes™ Scoring Software, version 4.5.1 or a later version. In case of missingness the Full Missing Score Estimation (MSE) method or Item Response Theory (IRT) will be used, if applicable, for imputation of missing values . SF-36v2 questions 2, the health domain scale T-scores, PCS T-scores and MCS T-scores will be derived using OPTUM scoring software (Third party vendor).

#### **8.4.2 Missing data**

The score estimation techniques will use all missing data, OPTUM scoring software is able to input the missing scale scores and component scores and estimate the score even some items are missing.

### **8.5. PRO Analysis Methods**

#### **8.5.1 Baseline**

The Day 1 ePRO data have been recorded few minutes after first administration dose, as these time differences between dose administration (Day1) and ePRO data collection on Day 1 are very small and in order to have baseline values for all subjects with ePRO data on Day 1, ePRO baseline is defined as values before or on the date of the first administration dose (Day1).

#### **8.5.2 Analysis**

A descriptive statistic of the actual values and change from baseline values at each timepoint (including baseline and available analysis time point) for ePRO derived scores will be displayed. In addition, mean changes from baseline values and summary measures will be explored per subgroup including (treatment group, subject population and stratification factors).

Frequency tabulation (number and percentage) of the response categories of question #2 of the SF-36v2 instrument will be displayed per time point for each treatment group.

---

For the EQ-5D descriptive system, tabulation of the number and percentage of subjects per problem level and per dimension will be displayed per time point for each treatment group.

For MOS-CFS Cog-R each of the 6 dimensions (having difficulty in reasoning and solving problems, having difficulty doing activities involving concentration and thinking, becoming confused and starting several actions at a time, forgetting things that happened recently, having trouble keeping attention and reacting slowly to things that are said or done) will be tabulated per time point for each treatment group.

For HBQOL questionnaires, tabulation of the number and percentage of subjects per dimension scale will be displayed per time point for each treatment group.

Tabulation of the number (and percentage) of subjects with clinically important improvement / worsening will be presented for SF-36v2, EQ-5D VAS and MOS-CFS Cog-R. There are no established thresholds for HBQOL. The clinically important thresholds are defined in the table below:

PRO Instrument	Mean Change from baseline, threshold	Individual Subject's Change from baseline, threshold
SF-36v2		
PCS	≥5 points	≥5 points
MCS	≥5 points	≥5 points
8 domain scores (T-scores)	≥5 points	≥5 points
EQ-5D VAS score		
	≥10 points	≥10 points
HBQOL	No threshold	No threshold
MOS-COG-R	≥5 point	≥5 point
This change refers to either an increase or a decrease >= threshold		

---

A cumulative distribution function will be drawn at different time points of the changes from baseline (Week 4 (for EQ-5D-5L and HQoL), Week 8(for SF-36v2 and MOS-CFS Cog-R), EOT and the follow-up assessments).

In addition, effect sizes will be calculated to measure the magnitude of difference between means in all different treatment groups using a mixed effect model for repeated measurement, including treatment groups, different analysis time points (treated as discrete/categorical) and their interaction as fixed effects and subject as random effect in the model.

Lsmeans of the change from baseline at each analysis time points with estimates, SE, 95% CI, type 3 p-values will be presented.

A graphical representation will be presented for each of the questionnaire results including the questionnaire different time points on the x-axis and adjusted mean change from baseline and SE on the y-axis.

---

## **9. PHARMACOKINETIC/PHARMACODYNAMIC ANALYSIS**

Descriptive statistics (n, mean, SD, coefficient of variation, geometric mean, Q1, Q2, median, minimum, and maximum) will be calculated for the plasma concentrations of total JNJ-56136379 and/or NA (ETV or TDF), as applicable, and for the derived plasma and urine pharmacokinetic parameters. Actual and/or dose-normalized pharmacokinetic parameters will be graphically displayed for JNJ-56136379 and NA (ETV or TDF) when administered alone or in combination

A listing for plasma concentrations and pharmacokinetic parameters of those subjects who discontinued the study for an AE, or who experienced an AE  $\geq$ grade 3, or an SAE will be provided.

---

## APPENDIX 1: SAS PROGRAM FOR SAMPLE IMPLEMENTATION OF BAYESIAN MODEL

```
*-----;
* SAMPLE IMPLEMENTATION OF BAYESIAN EFFICACY ANALYSIS USING PROC MCMC ;
* Subject Popn: Currently Not Being Treated HBeAg+ ;
* MAP Prior: 0.7447 N(-0.3059, 0.01892) + 0.2553 N(-0.3122, 0.05255) ;
* Prior: MAP Prior ;
* Data: nS=4, nE=12 (simulated for illustration - to be replaced with actual trial data) ;
*-----;

** Analysis will be done by HBeAG status;
/**/
Virologically suppressed population: HBeAG = Positive
2 number of components in the mixture
    Frist comp mean parameter (std)= 0.3809 N(-0.06528, 0.01440)
    Second comp mean parameter (std)= 0.6191 N(-0.05667, 0.004036)

With:
0.3809 , 0.6191: weights of the two components (should add up to 1)
-0.3059, -0.3122: the two means of each component
    Sqrt(0.01892),sqrt(0.05255)): standard deviations of each of the two
components

Virologically suppressed population: HBeAg = Negative
2: number of components in the mixture
    Frist comp mean parameter (std)= 0.3809 N(-0.06528, 0.01440)
    Second comp mean parameter (std)= 0.6191 N(-0.05667, 0.004036)

Currently not being treated population: HBeAG = Positive
2: number of components in the mixture
    Frist comp mean parameter (std)= 0.7447 N(-0.3059, 0.01892)
    Secd comp mean parameter (std)= 0.2553 N(-0.3122, 0.05255)

Currently not being treated population: HBeAg = Negative
3: number of components in the mixture
    Frist components mean parameter (std)= 0.0177 N(-0.01450, 0.1045)
    Secd components mean parameter (std)= 0.5728 N(-0.00925, 0.005850)
    Third components mean parameter (std)= 0.4095 N(-0.01308, 0.01988)

/* small difference*/
data current;
retain id trtcd trt y;
id = n ;
input trt $ y;
if trt="EXP" then trtcd=1;
if trt="SOC" then trtcd=0;
cards;
EXP   -0.42049058
EXP   0.002817434
EXP   0.203074308
EXP   -2.80207664
EXP   -0.610704519
EXP   -0.679890698
EXP   -0.991367774
EXP   -0.525054268
EXP   -0.117132573
```

---

```

EXP    -0.817565631
EXP    -0.689900046
EXP    -0.431818543
SOC    0.585224988
SOC    -0.488106494
SOC    -0.307694965
SOC    -0.686285388
;
run;

/* strong difference*/
data current;
retain id trtcd trt y;
id = n ;
input trt $ y;
if trt="EXP" then trtcd=1;
if trt="SOC" then trtcd=0;
cards;
EXP    -0.42049058
EXP    0.002817434
EXP    0.203074308
EXP    -2.80207664
EXP    -1.610704519
EXP    -1.679890698
EXP    -1.991367774
EXP    -1.525054268
EXP    -1.117132573
EXP    -1.817565631
EXP    -1.689900046
EXP    -1.431818543
SOC    0.585224988
SOC    -0.488106494
SOC    -0.307694965
SOC    -0.686285388
;
run;

ods listing close;
ods html path="%sysfunc(getoption(work))" gpath="%sysfunc(getoption(work))";
ods graphics on;

proc mcmc data=current outpost=out01 seed=123 nbi=100000 nmc=10000000 thin=100 plots=all
  diagnostics=all stats(alpha=0.1 percent=(5 10 20 50 80 90 95))
monitor=(mu_E mu_S s_E s_S delta pp1 pp2 pp3);
parms mu_E mu_S s_E s_S delta pp1 pp2 pp3;
prior mu_E ~ normal(0, var=100);
prior s: ~ igamma(0.01, s=0.01);
pdfmix = logpdf("NORMALMIX", mu_S, 2, 0.3809, 0.6191, -0.06528, -0.05667,
                 sqrt(0.01440), sqrt(0.004036));
prior mu_S ~ general(pdfmix);
delta = mu_E - mu_S;
pp1 = (delta < 0);
pp2 = (delta < -0.5);
pp3 = (delta < -1);

```

---

---

```
if TRT01A="JNJ6379 75 mg + NA" then llike =
logpdf("normal",chg,mu_E,s_E);
if TRT01A="Placebo 75 mg + NA" then llike =
logpdf("normal",chg,mu_S,s_S);
model general(llike);
run;

ods graphics off;
ods html close;
ods listing;
```

## APPENDIX 2: R CODE FOR DOSE RESPONSE

```
library(DoseFinding)
dose.range=c(0,dose.rat,1)
models=Mods (linear=NULL,emax=0.20,exponential=0.18,doses=c(dose.r
ange),maxEff=1,placEff=0)
optContr (models,w=c (2/8,3/8,3/8))

library(DoseFinding)
dose.range=c(0,dose.rat,1)
models=Mods (linear=NULL,emax=0.20,exponential=0.18,doses=c(dose.r
ange),maxEff=1,placEff=0)
optContr (models,w=c (2/8,3/8,3/8))
MCTtest (dose=dose.range,models=models,type="general",resp=c (mean.
placebo,mean.low,mean.high),S=matrix (nrow=3,ncol=3,c (se.mean.plac
ebo^2,0,0,0,se.mean.low^2,0,0,0,se.mean.high^2))
```

---

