### **11.2. Sample Size Determination**

As this is an exploratory, hypothesis-generating study, no formal statistical hypothesis testing will be performed.

The adequacy of the sample size for the different parts of the study has been assessed by evaluating the performance of the planned analyses on the primary endpoint (mean HBsAg change from baseline at Week 24) comparing JNJ-56136379+NA with placebo+NA as outlined in Section 11.3. Baseline is defined as the last assessment prior to the first intake of study drugs (JNJ-56136379/NA/placebo) on Day 1.

Power was assessed using simulations (10,000 replicates per scenario) with means and SDs for the placebo+NA and JNJ-56136379+NA arms as listed in Table 7. Mean and SD may depend on HBeAg status at baseline and prior treatment (currently not being treated or virologically

suppressed). Treatment with JNJ-56136379 was set to result in one additional mean  $\log_{10}$  IU/mL decline in HBsAg from baseline at Week 24. Data were simulated from mixture distributions which reflect the skewed distributions which are typical HBsAg decline data. It is assumed that HBeAg-positive subjects will enroll slower than HBeAg-negative subjects, particularly in virologically suppressed subjects. Therefore, the aim is to have at least 40% HBeAg-positive subjects currently not being treated and 30% HBeAg-positive virologically suppressed subjects.

For the dose-response modeling (multiple contrast test) the placebo+NA arms of Parts A and B will be pooled and the HBeAg subgroups will be pooled per dose. Assuming the treatment effect does not depend on HBeAg status, the power to detect a dose-response signal ( $\alpha=0.10$ , one-sided) depends on the assumed effect of the low dose: ranging from 91% when the low dose has no effect to 99% when the low dose has the same effect as the high dose. Sensitivity analyses will be done investigating differences across Parts A and B and differences between the two HBeAg subgroups.

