### **1.5. Sample Size Justification**

See CTP, Section 11.2.

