**Figure X2: Multiple Contrast Test Candidate Model Set**

The significance of the dose-response signal associated with each candidate model will be determined using trend tests with model-specific optimal contrast coefficients. The maximum of the candidate model trend test statistics will be used to evaluate the presence of a dose-response signal, properly accounting for multiplicity at an overall level of 5% (1-sided) using MCP-Mod methodology.

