### **Multiple Contrast Test**

The MCT will be executed using the MCTtest-function of the R-package DoseFinding (version 0.9-16) using the R code (See **APPENDIX 2**). In this code, the low dose is expressed relative to the high dose. At the time of execution, the scalar “dose.rat” will be replaced by ratio of the low dose over the high dose.

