#### Input:

1. mean.placebo = mean Week 24 HBsAg change from baseline in the placebo-group (arms pooled over Part A and Part B).
2. mean.low.dose = mean Week 24 HBsAg change from baseline in the JNJ379+NA group of |Part A
3. mean.high.dose = mean Week 24 HBsAg change from baseline in the JNJ379+NA group of |Part B
4. se.mean.placebo = standard error of the mean Week 24 HBsAg change from baseline in the placebo-group (arms pooled over Part A and Part B)
5. se.low.dose = standard error of the mean Week 24 HBsAg change from baseline in the JNJ379+NA group of Part A
6. se.high.dose = standard error of the mean Week 24 HBsAg change from baseline in the JNJ379+NA group of Part B

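### SAP Appendix 2 codes the one-sided dose-response test for rising HBsAg, the wrong tail for a planned decline; separately, the SAP tests at 5% but relies on power computed at 10%.

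*SAP*

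**What the plan says.** - **Candidate shapes.** SAP Appendix 2 defines linear, Emax and exponential shapes with "maxEff=1,placEff=0": 0 on placebo, rising to +1 at the high dose.
- **Inputs.** SAP 5.4 passes the group means unchanged, for example "mean.placebo = mean Week 24 HBsAg change from baseline in the placebo-group (arms pooled over Part A and Part B").
- **Execution.** SAP 5.4 states: "The MCT will be executed using the MCTtest-function of the R-package DoseFinding (version 0.9-16) using the R code". The `MCTtest` call in Appendix 2 names neither an alternative nor an alpha.
- **Decision rule.** SAP 5.4 uses the largest of the trend statistics, "properly accounting for multiplicity at an overall level of 5% (1-sided) using MCP-Mod methodology".
- **Planned direction.** Protocol 11.2 assumes that JNJ-56136379 adds one log10 "IU/mL decline in HBsAg from baseline at Week 24".
- **Power.** For sample size, SAP 1.5 says only "See CTP, Section 11.2". That section gives power at one-sided alpha 0.10, "ranging from 91% when the low dose has no effect to 99% when the low dose has the same effect as the high dose".

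**The concern.** With rising shapes, each optimal contrast is negative on placebo and positive on the high dose. Applied to changes that become more negative with dose, every contrast statistic has a negative expectation, and a one-sided test on the maximum looks only at the upper tail. A working drug would give no signal; a rise in HBsAg would give one.

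The rest of the SAP has the direction right: the Bayesian analysis in SAP 5.2.1.2 and Appendix 1 counts a difference below 0 as benefit. Appendix 2 is the exception. The wrong sign would raise no error message; the program would simply report that no dose-response was found.

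The level is a second, independent point. Power computed at 10% does not describe a test run at 5%, and the SAP restates no power for its own level.

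**Working it through.** **Inputs**
- Group sizes per population: placebo+NA 10 in each part, pooled to 20; JNJ-56136379+NA 30 at each dose (Protocol 3.1). This matches the 2:3:3 weights in Appendix 2 and the by-population analysis in SAP 5.4.
- Doses relative to the high dose: 0, 75/250 = 0.3, and 1.
- Protocol Table 7: control -0.05 (SD 0.4), or -0.35 (SD 0.6) in untreated HBeAg-positive subjects; active mean 1 log10 lower, SD 2.16.
- The mixture behind the protocol's simulations is not given, so it has to be assumed.

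**Step 1: shape values at the low dose (high dose = 1)**
- Linear: 0.30.
- Emax, ED50 0.20: 1.2 × 0.3/(0.2 + 0.3) = 0.72.
- Exponential, delta 0.18: (e^(0.3/0.18) - 1)/(e^(1/0.18) - 1) = 0.017.

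**Step 2: direction of one contrast, worked by hand.** An optimal contrast is proportional to weight × (shape - weighted mean shape). For the linear shape with weights 2/8, 3/8, 3/8:
- Weighted mean: 0.375 × 0.3 + 0.375 × 1 = 0.4875.
- Contrast: 0.25 × (0 - 0.4875) = -0.1219 on placebo; 0.375 × (0.3 - 0.4875) = -0.0703 on the low dose; 0.375 × (1 - 0.4875) = +0.1922 on the high dose.
- Planned means, low dose inactive: -0.05, -0.05, -1.05. The contrast sums to zero, so its value is 0.1922 × (-1) = -0.1922.
- Variances of the means: 0.4²/20 = 0.008 and 2.16²/30 = 0.1555. SE = √(0.1219² × 0.008 + 0.0703² × 0.1555 + 0.1922² × 0.1555) = 0.081.
- Statistic: -0.1922/0.081, about -2.4.

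With contrasts weighted by 1/SE² and SD 2.16 at both doses, the expected statistics (linear/Emax/exponential) are -2.37/-1.99/-2.48 when the low dose is inactive, and -2.97/-3.37/-2.40 when the doses are equal. Across all settings examined, mean statistics run from -0.57 to -3.46. The one-sided critical values of the maximum are positive: 1.37-1.64 at 10% and 1.73-1.98 at 5%.

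**Step 3: the test as coded.** The simulations covered both contrast choices (2:3:3 weights or weights from S), normal and skewed mixture data, and an inactive low dose with SD 2.16 or the control SD. The chance of a signal under the planned decline was at most about 1.8% at 10% and 0.8% at 5%.

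**Step 4: the protocol's power figure, then the same test at 5%, with the sign corrected.** Each cell gives power with the low dose inactive / with the low dose equal to the high dose.

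| Data assumed (control mean -0.05) | 10% one-sided | 5% one-sided |
|---|---|---|
| Protocol 11.2 | 91% / 99% | not stated |
| Mixture, 20-30% responders, S-based contrasts, inactive low dose with control SD | 91-92% / 98% | 80-81% / 96-97% |
| Mixture, 35% responders, S-based contrasts, low-dose SD 2.16 | 91.8% / 98.2% | 83.4% / 95.9% |
| Normal, both contrast choices | 82-88% / 91-97% | 72-80% / 84-94% |

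The mixtures take the stated share of treated subjects as responders and match the Table 7 mean and SD. They reproduce the protocol's figures to within about 1 point; normal data do not reach 91%.

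**The case against.** The strongest points on the other side:

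- **The block cannot run exactly as printed.** `dose.rat` is a placeholder and four variable names differ from the SAP 5.4 list. For example, the list has "se.low.dose = standard error of the mean Week 24 HBsAg change from baseline", while the code expects `se.mean.low`. The final call also appears to lack a closing parenthesis, which may be an effect of reading the PDF. This is true, but none of these repairs touches the sign.
- **A second implementation is named.** SAP Section 1 says an MCPMod procedure for SAS will also be used, with no sign convention printed. So the result in Step 3 is shown for the R code only. SAP 5.4 nonetheless commits to that R code.
- **The prose is neutral.** SAP 5.4 describes shapes by size of effect, and `maxEff=1` could be a unit scaling. That would be harmless if declines were entered as positive numbers, but the input list gives raw changes.
- **The tail is inferred.** The call names no alternative and the R package was not available to run. The upper tail is read from SAP 5.4, which specifies a one-sided test on the maximum.
- **Other analyses compare the doses with control.** The MMRM and Bayesian results would show negative differences, so the contradiction might be noticed. They are pairwise comparisons, though, and not a dose-response trend test.
- **The 5% level is permitted.** Protocol 11.3.1 sets no level for this test, 0.10 appears only with the power, and the study plans no formal hypothesis testing. This stands: the level is not a breach. What remains is that the quoted power belongs to a different level.
- **The mixture is unknown.** This also stands. The 5% power figures are ranges under assumptions; the sign conclusion does not depend on them.

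**Conclusion.** Both parts hold, and this should be fixed. The sign error follows from the documents themselves: rising shapes, raw changes as inputs, a one-sided maximum, and no reversal anywhere. Run with that sign, the test would almost never detect the decline it was planned for, signalling in under 2% of trials at either level, and it would report a rise in HBsAg as a signal.

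With the sign corrected, power at the SAP's 5% level is about 80-84% where the protocol quotes 91%, and about 96-97% where it quotes 99%. This assumes 20/30/30 subjects per population, a dose ratio of 0.3, the Table 7 SDs, and mixtures chosen to come close to the protocol's own figures.

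The consequence is confined to the dose-response conclusion of an exploratory study. The primary Bayesian comparison is not affected.

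**What to change.** In Appendix 2 and SAP 5.4:

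1. Set `maxEff=-1` in `Mods()`, or negate the three input means, but not both. Apply the same direction in the SAS procedure if it is used.
2. State `alternative='one.sided'` and the alpha explicitly in `MCTtest`.
3. Make level and power agree: either test at one-sided 10%, or keep 5% and restate the power at 5%, giving the mixture used.
4. Enter `dose.rat` = 75/250 = 0.3. The SAP already provides for this replacement, and the dose is now known.
5. Use one set of variable names: the SAP 5.4 list has `mean.low.dose`, `mean.high.dose`, `se.low.dose` and `se.high.dose`; the code has `mean.low`, `mean.high`, `se.mean.low` and `se.mean.high`. Check the closing parenthesis of the call.
6. Say whether the 2:3:3 contrasts apply. The `optContr` result is neither stored nor passed to `MCTtest`.

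The cost is edits to one code block and one sentence on level or power, plus a rerun of the power simulation if 5% is kept. No patients, data or trial procedures are affected.
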